2.2.2 Safety Set

The Safety Set (SS) includes all patients who received at least one dose of study drug (osilodrostat or placebo). Patients will be analyzed according to the study drug received, where treatment received is defined as the randomized/assigned treatment if the patient took at least one dose of that treatment or the first treatment received if the randomized/assigned treatment was never received.

2.2.3 Per-Protocol Set

Per-Protocol Set (PPS) consists of a subset of the patients in the FAS who are compliant with the requirements of the Clinical Study Protocol. The following protocol deviations will lead to exclusion from PPS.

- Informed consent for core phase not documented
- mUFC or ACTH related inclusion criteria not met
- Pituitary source of excess ACTH is not confirmed

- Cushing's disease confirmation is missing
- Pituitary surgery related inclusion criteria not met
- Pituitary irradiation related inclusion criteria not met
- Washout period related inclusion criteria not met
- Participation in another trial with an investigational drug does meet the exclusion criteria
- Subject pregnant or lactating at study entry does mee the exclusion criteria
- Subject's history of inherited syndrome as cause for hormone over secretion does meet the exclusion criteria
- Subject's medical history of Cushing's syndrome due to ectopic ACTH secretion or ACTH-independent (adrenal) Cushing's syndrome does meet the exclusion criteria
- Subject's moderate or severe renal impairment does meet the exclusion criteria
- Subject met the discontinuation criteria, but was not discontinued from the trial *
- Subject took a prohibited concomitant medication **
- *if PD occurs before Week 12, exclude from PPS, if occurs between Week 12 and Week 36, exclude from PPS for key secondary analysis
- **if PD occurs between Week 12 and Week 36, exclude from PPS for key secondary analysis. Not applicable for primary analysis.

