6.4.3 Prohibited concomitant therapy

Use of the following concomitant medication is prohibited during the study:

- Other drug treatments for Cushing's disease;
- Medications with a "known risk to cause Torsades des Pointes (TdP)" and "possible risk to cause TdP"
- Eplerenone and glucocorticoids, except under certain conditions:
 - Eplerenone may be used if necessary in acute post-myocardial infarction management, and in the event of refractory hypokalemia in patients with hypertension or edema; glucocorticoids may be used as required for the short-term treatment of hypocortisolism or adrenal insufficiency.
- Glucocorticoids (except under certain conditions as explained below in [Section 6.4.3.2](#)).

6.4.3.1 Concomitant medications with a "Known risk to cause TdP" and with a "Possible risk to cause TdP".

Preclinical data and preliminary clinical data indicate that there is a risk of QTc prolongation in humans (see [Section 8.1.3.1](#)). Therefore, the use of medications with a "Known risk to cause TdP" and with a "Possible risk to cause TdP" concomitantly with osilodrostat is prohibited.

If a patient requires a long-term medication from the two categories mentioned above, and there is no appropriate alternative medication available, they should be discontinued from the study.

However, if a patient requires such a drug for short-term therapy, e.g., antibiotics for active infection, then osilodrostat may be interrupted temporarily while this drug is administered after a thorough risk-benefit assessment. This does not require the patient to discontinue from the study prematurely. Washout periods for osilodrostat and the short-term prohibited drug in many cases may not be possible; this is acceptable if the benefit of the drug outweighs the risk of withholding osilodrostat therapy in the investigator's judgment. In such cases, a discussion with the Novartis Medical Monitor is recommended.

Please refer to [Appendix 2](#) for an e-link to a list of medications that have a "Known risk to cause TdP" and "Possible risk to cause TdP". Investigators are advised to utilize this website when considering the addition of a new concomitant medication, as the lists are periodically updated.

If necessary, a discussion can be held with the Novartis Medical Monitor when considering the use of medications with a “Known risk to cause TdP” and with a “Possible risk to cause TdP”

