The investigator must discontinue study drug for a given patient if he/she believes that continuation would be detrimental to the patient's well-being. The investigator must also contact the IRT to register the patient's discontinuation from study drug.

Patients must discontinue study drug if any of the following occur:

- Emergence of the following adverse events:
- hypertension defined as office mean supine systolic BP > 180 mmHg or mean supine diastolic BP > 110 mmHg (confirmed and persistent*).
- Any of the following laboratory abnormalities (confirmed):
 - hyperkalemia (serum potassium > 6.0 mmol/L).
 - hypokalemia (serum potassium < 2.8 mmol/L).
- Any of the following laboratory abnormalities (confirmed and persistent*):
 - hyperkalemia (serum potassium > 5.5 mmol/L).
 - hypokalemia (serum potassium < 3.0 mmol/L).
 - hyponatremia (serum sodium < 130 mmol/L).
 - hyperglycemia (fasting plasma glucose \geq 15.0 mmol/L).

* Persistent is defined as unresolved with osilodrostat dose change or after adjustments to other concomitant medications targeting the co-morbidity in question.

- Abnormal liver function as described in [Table 6-2](#).
- Mean QTcF > 500 msec, if the QTc value is confirmed by a cardiologist (see [Section 7.2.2.7](#)).

- Mean QTcF > 480 msec, if the investigator determines it is no longer safe for the patient to continue in the study, based on ECGs, cardiac examination, and recommendation from a cardiologist (see [Section 7.2.2.7](#)).
- Mean increase in QTcF > 30 msec from the mean baseline value at 1.5h post-first dose or the QTcF is > 480 msec at Day 1.
- QTcF increase > 60 msec from the pre-dose measurement earlier during the same visit.
- Pituitary tumor growth, if symptomatic or complicated by compression of the optic chiasm or other structures in and near the sella turcica (visual field loss, cranial nerve palsies, diplopia) and confirmed by MRI of the pituitary (see [Section 7.2.2.5](#)).
- Pregnancy.
- Use of prohibited treatment (refer to [Section 6.4.3](#)).
- Any other protocol deviation that results in a significant risk to the patient's safety.

The appropriate personnel from the site and Novartis will assess whether study drug should be discontinued for any patient whose treatment code has been broken inadvertently for any reason.

The investigator must also contact the IRT to register the patient's discontinuation from study drug within 2 days.

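### Per-protocol set for the Week 12 endpoint: the prohibited-medication note waives an exclusion that the neighbouring discontinuation item imposes, so membership is inconsistent for patients who took another Cushing's drug in Period 1

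*SAP*

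**What the plan says.** Core SAP 2.2.3 (SAP released 01-Apr-2019) introduces its list with "The following protocol deviations will lead to exclusion from PPS". Two adjacent items carry timing notes.

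- **Single-star item:** "Subject met the discontinuation criteria, but was not discontinued from the trial". Its note reads: "if PD occurs before Week 12, exclude from PPS, if occurs between Week 12 and Week 36, exclude from PPS for key secondary analysis".
- **Double-star item:** the patient took a prohibited concomitant medication. Its note reads: "if PD occurs between Week 12 and Week 36, exclude from PPS for key secondary analysis. Not applicable for primary analysis". The closing words, "Not applicable for primary analysis", are the ones at issue.

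The protocol connects the two. Section 6.4.3 opens its list of prohibited therapy with "Other drug treatments for" Cushing's disease and attaches no exception to that entry. Section 7.1.4 states "Patients must discontinue study drug if any of the following occur", and the list that follows includes "Use of prohibited treatment", with a reference back to 6.4.3.

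The PPS is used for the primary endpoint in core SAP 2.5.4, where the stratified exact CMH test and Fisher's exact test are repeated as supportive analyses. The primary test itself uses the full analysis set (FAS, SAP 2.5.2).

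**The concern.** The endpoint is mUFC at or below the upper limit of normal, and another Cushing's drug acts on mUFC directly. A per-protocol analysis of that endpoint should not leave open whether patients taking such a drug are in the set. Here one note says the deviation does not count for the primary analysis, while the item beside it, read with protocol 7.1.4, says the patient is out. Core SAP section 4, which records changes from the protocol, does not mention the point.

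The waiver also sits oddly with the rest of the list. A patient who did not meet the washout criterion, and so may carry residual effect of a previous Cushing's drug, is excluded. Under the double-star note, one taking such a drug up to Week 12 is not.

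At stake is how far the Week 12 PPS result supports the FAS result. Two programmers working from the same text could build different sets.

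**Working it through.** **Tracing one patient through the rules.** Take a patient who used another Cushing's drug before Week 12.

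| Situation | Single-star item | Double-star item |
|---|---|---|
| Stayed on study drug | Met a 7.1.4 criterion before Week 12 and was not discontinued: excluded | Switched off for the primary analysis: not excluded |
| Discontinued before Week 12 | Does not apply | Switched off; the patient counts as a non-responder (SAP 2.5.1, 2.5.3) |

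The inconsistency is confined to the first row. A wording mismatch blurs the boundary: the single-star item speaks of discontinuation from the trial, whereas 7.1.4 requires stopping study drug and says that such patients are not to be regarded as withdrawn from the study. Read literally, someone who stopped study drug as required but stayed for follow-up could be caught by the single-star item.

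**The plan's figure.** The plan gives no figure for PPS membership. Its background power statement (60% against 15%, 42 and 21 patients, one-sided 0.025, 91%) was checked by full enumeration of the exact CMH test with strata of 8+4 and 34+17 patients. The result is 92.2%, close enough that the planning inputs are not in question.

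**Possible size.** The number of affected patients is not in the documents, so k = 1 to 3 is an assumption. The start is a PPS of 42 and 21 patients with responders near the planned rates: 0.60 × 42 ≈ 25 and 0.15 × 21 ≈ 3. The difference is 25/42 − 3/21 = 59.5% − 14.3% = 45.2 points, with one-sided Fisher p = 0.0006.

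*Contaminated placebo patients.* Suppose k further placebo patients are responders only because of another drug. Keeping them gives 25/42 against (3+k)/21; excluding them gives 25/42 against 3/(21−k).

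| k | Kept: points (p) | Excluded: points (p) |
|---|---|---|
| 1 | 59.5 − 19.0 = 40.5 (0.0023) | 59.5 − 15.0 = 44.5 (0.0009) |
| 2 | 59.5 − 23.8 = 35.7 (0.0073) | 59.5 − 15.8 = 43.7 (0.0015) |
| 3 | 59.5 − 28.6 = 31.0 (0.0195) | 59.5 − 16.7 = 42.9 (0.0023) |

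*Contaminated osilodrostat patients.* Keeping them gives (25+k)/42 against 3/21; excluding them gives 25/(42−k) against 3/21.

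| k | Kept: points | Excluded: points |
|---|---|---|
| 1 | 61.9 − 14.3 = 47.6 | 61.0 − 14.3 = 46.7 |
| 2 | 64.3 − 14.3 = 50.0 | 62.5 − 14.3 = 48.2 |
| 3 | 66.7 − 14.3 = 52.4 | 64.1 − 14.3 = 49.8 |

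At k = 3 the choice of rule moves the estimate down by 42.9 − 31.0 = 11.9 points in the first case and up by 52.4 − 49.8 = 2.6 points in the second. The placebo case moves further because that arm is half the size.

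**The case against.** The best defence is that the list gives sufficient reasons for exclusion. An item that is not applicable does not order anyone to be kept, so the single-star item still removes a patient who should have stopped study drug and did not. The two notes do not clash on their face; the tension appears only through protocol 7.1.4. That stands as far as it goes: a reader might infer that the SAP definitely keeps these patients, and the text does not establish that. But the SAP never says that one item is enough despite a waiver in another, and on this reading the waiver is overridden for exactly these patients.

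A narrower reading is that the waiver means only that use in Weeks 12 to 36 is irrelevant at Week 12. It fits poorly, because the single-star note states a rule for the time before Week 12 and the double-star note has none. Period 1 use would still be unaddressed.

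It is also fair that prohibited medication covers more than Cushing's drugs. Protocol 6.4.3 and its subsections allow short-term use of drugs with torsades risk while osilodrostat is interrupted, and eplerenone and glucocorticoids under conditions. Not excluding every such user from a small Week 12 PPS is defensible, and protocol 10.1.3 leaves the deviation criteria to be settled before database lock. None of this covers other Cushing's drugs.

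Finally, the PPS tests are supportive, and in the worst placebo case above p = 0.0195 is still below 0.025. That limits the consequence but does not settle who belongs in the set.

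**Conclusion.** The point holds as an inconsistency in the definition of the primary-endpoint PPS. It concerns patients who took another Cushing's drug before Week 12 and were not discontinued: the double-star note waives the exclusion that the single-star item imposes through protocol 6.4.3 and 7.1.4.

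If the waiver is followed, the supportive Week 12 estimate can be diluted by placebo patients or inflated by osilodrostat patients. With one to three affected patients in one arm, the difference between the rules runs from 44.5 − 40.5 = 4.0 to 11.9 points downward, or from 47.6 − 46.7 = 0.9 to 2.6 points upward. These figures assume responders near the planned rates and that every affected patient responds because of the other drug. The actual number could be zero.

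A reader might go further and infer that the primary result is compromised, or that the rule favours one arm. The documents support neither. The primary test uses the FAS, patients who discontinued before Week 12 are non-responders, and the direction depends on which arm the patients are in.

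**What to change.** Leave the existing Week 12 to 36 exclusion for any prohibited medication (key secondary PPS) as it is. Replace the closing waiver in the double-star note with:

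> Use of another drug treatment for Cushing's disease (protocol 6.4.3, first item) before the Week 12 assessment excludes the patient from the PPS for the primary analysis.

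Then add three clarifications to SAP 2.2.3:

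1. Any one listed deviation is enough to exclude.
2. How the single-star item applies to the other prohibited drugs, given the conditional allowances in protocol 6.4.3.
3. Whether discontinuation in the single-star item means from study drug or from the trial, aligned with protocol 7.1.4.

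The cost is a few lines of SAP text and possibly a few patients fewer in the primary PPS. Dosing and patient management do not change.

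The final-analysis SAP of 01-Dec-2020 says that the primary and key secondary results were already reported in the interim study report and that only the FAS and safety set are carried forward. If so, a change before lock is no longer possible. The remedy is then to state which rule was used to build the Week 12 PPS, give the number of affected patients by arm, and show the PPS result with and without them.

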2.2.4 Pharmacokinetic analysis set

The pharmacokinetic analysis set (PAS) consists of all patients who received at least one dose of osilodrostat and have at least one evaluable pharmacokinetic concentration (post-first-dose) at any visit.

A PK concentration is considered as non evaluable if:

- The patient didn't receive the incident dose (last dose administered prior to PK collection) as planned per protocol, or
- If the elapsed time between PK sample and prior dose didn't fall within acceptable window:
 - pre-dose samples within 0.5 h before dose administration, and within 9h to 15h after the previous dose
 - post-dose samples with elapsed time within nominal time range (i.e. within 1h to 2h),
 - 12h PK sample with elapsed time within 9h to 15h after previous dose.
- Or if vomiting occurs within 4 hours after the last intake prior to the PK sample draw.

Additionally, a PK concentration or parameter can be considered non-evaluable as per scientific judgment of the clinical pharmacology expert; reasons will be documented. Such PK concentration and parameter will be excluded from PK [REDACTED] tables/figures, but will be included in listings with flags and reasons for exclusion.

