6.2.1.3 Intermediate doses for dose adjustment

The preferred doses for either up or down-titration are the standard recommended doses of 2, 5, 10 and 20 mg b.i.d. during Period 1. The preferred intermediate doses are: 3, 7, and 15 mg b.i.d., but other doses may be selected if necessary.

Examples of the appropriate use of intermediate study drug doses are described below:

- A patient previously down titrated from a higher dose for signs and symptoms of adrenal insufficiency to the next lower standard dose (e.g., down titrated from 10 mg b.i.d. to 5 mg b.i.d.), and who experienced an increase in mUFC > ULN, or developed signs and symptoms of hypercortisolism at the lower dose, may be up titrated to an intermediate dose (e.g. 7 mg b.i.d., or, if needed, another intermediate dose between 5 mg and 10 mg b.i.d.) to optimize control.
- A patient who had mUFC > ULN, with or without signs and symptoms of hypercortisolism at one dose, and subsequently had mUFC < LLN or close to the LLN, accompanied by signs and symptoms of hypocortisolism at the next standard higher dose (e.g., after up-titration from 5 mg b.i.d. to 10 mg b.i.d.) may be down titrated to an intermediate dose (e.g., 7 mg b.i.d., or, if needed, other doses between 5 mg and 10 mg b.i.d.) to optimize control.

In patients treated with either osilodrostat or placebo, the study drug could be down-titrated to a dose lower than 2 mg b.i.d., if indicated. In addition, doses of 1 mg b.i.d. or lower can be used, e.g., 1 mg q.d. or 1mg q.o.d. (every other day), if needed for patients that are sensitive to osilodrostat. Importantly, only placebo-treated patients with mUFC < 1.5 x ULN will be down-titrated to doses below 2 mg b.i.d., to avoid unblinding and prolonged hypercortisolism after the Week 12 visit for patients with severely uncontrolled hypercortisolism.

The IEs, investigators, and other site staff should be aware that the use of non-standard doses increases the complexity of dispensing drug to the patient, and self-administration of drug by the patient (see [Section 6.6](#) for details).

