6.6.1 Study drug packaging and labeling

Osilodrostat/placebo will be supplied as film coated tablets packaged in bottles.

The study medication packaging has a 2-part label. A unique medication number is printed on each part of this label which corresponds to one of the treatment arms and a dose. Responsible site personnel will identify the study drug package(s) to dispense to the patient by using the IRT and obtaining the medication number(s). Site personnel will add the subject number onto the label. Immediately before dispensing the package to the patient, site personnel will detach the outer part of the label from the packaging and affix it to the source document (Drug Label Form) for that patient's unique subject number.

Medication labels will be in the local language and comply with the legal requirements of each country. They will include storage conditions for the drug and the medication number but no information about the patient.

Table 6-4 Packaging and labeling

Study drugs	Packaging	Labeling (and dosing frequency)
Osilodrostat (LCI699) or placebo (1 mg, 5 mg, 10 mg and 20 mg)	Tablets in bottles with labels	LCI699, LCI699/Placebo (b.i.d., o.d., once every other day)

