^a The following PK assessment windows are acceptable: pre-dose sample within 0.5 h before dose administration, ± 10 min for up to the 2 h timepoint, and within 0.5h before the 12h post dose sampling. If patient enters the extension phase of study, the 12 h post dose sampling should be taken prior to the first dose in the extension phase

[figure not shown]
^b For the PK pre-dose (trough) samples, the actual date and time of administration of the previous dose of study medication should also be recorded with appropriate PK collection number as indicated in the above table. The PK collection number series “1, 2, 3...” is for the osilodrostat dose administered on study visit day, while PK collection number series “201, 301, 401...” is for the previous osilodrostat dose the subject received prior to the collection of the PK pre-dose (trough) sample

[figure not shown]

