2.9 Pharmacokinetic endpoints

The PAS will be used in all pharmacokinetic data analysis and summary statistics.

As sparse pharmacokinetic sampling is performed in this study, traditional non-compartmental analysis will not be performed to calculate pharmacokinetic parameters. Plasma concentration data of osilodrostat will be listed by subject, visit, incident dose and nominal sampling times. Descriptive statistics of plasma concentrations will be provided by incident dose, visit and nominal sampling times, and will include arithmetic and geometric mean, median, SD, CV%, geometric CV%, minimum and maximum. Zero concentrations will not be included in the geometric mean calculation.

Listing of all PK parameters will be provided by patient and visit:

- Ctrough as defined by pre-dose concentration collected within 0.5h prior to dosing and within 9h to 15h after the previous dose and
- and Cmax, defined as concentration collection within 1-2hr post-dose.

Plasma concentrations of osilodrostat will be expressed in ng/mL. Missing concentration values will be labeled as such in data listings. Concentrations below the limit of quantitation (LLOQ) will be treated as zero in summary statistics and reported as zero in data listings.

[REDACTED]

[figure not shown]
[REDACTED]

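### The core SAP's trough window fits twice-daily dosing only, so correctly timed troughs on 1 mg once daily or every other day drop out of the PK summaries; separately, its post-dose window is narrower than protocol Table 7-7

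*SAP*

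**What the plan says.** Core SAP 2.2.4 (April 2019) sets out when a PK concentration is non-evaluable. For troughs, the acceptable window is "pre-dose samples within 0.5 h before dose administration, and within 9h to 15h after the previous dose". Section 2.9 repeats it in the parameter definition: "Ctrough as defined by pre-dose concentration collected within 0.5h prior to dosing and within 9h to 15h after the previous dose". For the later draw, the acceptable samples are "post-dose samples with elapsed time within nominal time range (i.e. within 1h to 2h". Non-evaluable concentrations leave the PK tables and figures and remain in listings with a flag and a reason. The expert-judgement clause in 2.2.4 can add exclusions but cannot restore a sample. Section 2.9 summarises concentrations by incident dose, visit and nominal sampling time, not by regimen.

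Protocol 6.2.1.3 allows "1 mg q.d. or 1mg q.o.d. (every other day), if needed for patients that are sensitive to osilodrostat". Table 6-4 labels the supplies for "b.i.d., o.d., once every other day" use, Table 6-1 names 1 mg every other day as the lowest dose, and the footnote to the SAP's own Figure 1-1 lists both regimens.

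Protocol Table 7-7, footnote a, asks only that a pre-dose sample be taken within 0.5 h before dosing, with no limit on the time since the previous dose. For the other draws the tolerance is plus or minus "10 min for up to the 2 h timepoint, and within 0.5h before the 12h post dose sampling".

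**The concern.** The SAP's trough rule presumes a 12 h interval, but the protocol does not confine patients to one. A site that samples a once-daily or every-other-day patient exactly as Table 7-7 asks produces a value that the SAP then calls non-evaluable. PK exposure is a stated secondary objective, and the two regimens exist for patients who are sensitive to the drug. The exclusion is therefore linked to a patient characteristic and is not haphazard.

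The resulting table would not show the gap. The incident dose is 1 mg for 1 mg twice daily, once daily and every other day alike, so the 1 mg trough row would carry twice-daily visits only, with nothing in its label to say so.

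The post-dose mismatch is a second, independent matter: samples drawn within the protocol's tolerance are rejected at the analysis stage. The SAP history records an update of the PK collection windows, but SAP section 4, on changes to the protocol-specified analyses, does not mention it.

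**Working it through.** The plan gives no figure to reproduce, so the check compares intervals.

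**Trough window.** Inputs: acceptable time since previous dose 9–15 h (SAP 2.2.4, 2.9); sample drawn at most 0.5 h before dosing (SAP 2.2.4, Table 7-7); prescribed interval τ = 12, 24 or 48 h. An on-schedule trough falls between τ − 0.5 h and τ.

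| Regimen | τ | On-schedule trough | Inside 9–15 h? | Least excess over 15 h |
|---|---|---|---|---|
| twice daily | 12 h | 11.5–12 h | yes | none |
| once daily | 24 h | 23.5–24 h | no | 23.5 − 15 = 8.5 h |
| every other day | 48 h | 47.5–48 h | no | 47.5 − 15 = 32.5 h |

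Dosing slack does not rescue them. Protocol 6.1.1 treats a dose as missed once it is more than 4 h late. With the previous dose 4 h late and the next on time, the earliest trough is 24 − 4 − 0.5 = 19.5 h (once daily) or 48 − 4 − 0.5 = 43.5 h (every other day). Both still exceed 15 h.

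**Samples exposed to the rule.** Table 7-7 schedules on-treatment pre-dose draws at Weeks 2, 5, 8, 12, 14, 17, 20, 23, 26, 29, 32, 36, 40 and 44, which is 14. That is a ceiling from the schedule; the rule bites only at visits while the patient is on one of the two regimens. The 1–2 h draws stop after Week 29, so at Weeks 32, 36, 40 and 44 such a patient has no evaluable scheduled concentration. The 12 h sample at Week 48 can still pass.

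**Post-dose window.** Protocol: 60 − 10 = 50 min to 120 + 10 = 130 min, a width of 80 min. SAP: 60 to 120 min, a width of 60 min. Rejected: 80 − 60 = 20 min, and 20/80 = 25% of the protocol window. This is a share of the window, not of samples; the documents give no distribution of draw times.

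**Would the excluded troughs be measurable?** This is a rough check under assumptions. Start from the predicted mean steady-state Cmax of 174 ng/mL at 20 mg (protocol 1.2.1.2.4). Scale down to 1 mg by a factor f per halving of dose, with f from 2.0 (proportional) to 2.4 (upper end of the range in protocol 1.2.1.2.1). Let the concentration decay mono-exponentially from 1 h with a half-life of 3–5 h. Since log2(20) = 4.32, Cmax at 1 mg is 174/f^4.32, or 8.7 ng/mL (f = 2.0) to 3.96 ng/mL (f = 2.4).

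- At 24 h: lowest 3.96 × 2^(−23/3) = 0.02 ng/mL; highest 8.7 × 2^(−23/5) = 0.36 ng/mL. The range lies either side of the LLOQ of 0.10 ng/mL.
- At 48 h: lowest 3.96 × 2^(−47/3) = 0.0001 ng/mL; highest 8.7 × 2^(−47/5) = 0.013 ng/mL. All are below the LLOQ.

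**The case against.** The best defence is that little is lost. Protocol 2.2.3 expects only a small group below 2 mg twice daily by Week 12, and that group includes 1 mg twice daily and placebo patients. The PK analysis is sparse and descriptive. Every-other-day troughs are probably below the LLOQ. Because summaries are by incident dose and not regimen, a 1 mg row confined to about 12 h is at least coherent, and pooling 24 h and 48 h values into it would be worse. All of that stands. It argues for low severity and against pooling, but not for leaving the two regimens without any rule.

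On the post-dose side, an analysis window may differ from a collection tolerance, and 1–2 h matches the wording of the protocol endpoint. The update was recorded before database lock and unblinding. The SAP is also not stricter throughout: for the 12 h sample it accepts 9–15 h where the protocol asks for the last 0.5 h before 12 h. These points stand too, but the difference should still be declared.

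A reader might infer more than the documents support:

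- **That these patients' exposure data are missing.** The values stay in flagged listings. Study drug starts at 2 mg twice daily, so twice-daily troughs, valid 1–2 h samples and the Week 48 sample can still count, and the patients need not leave the PK analysis set.
- **That the post-dose mismatch adds to the trough loss.** It does not; it affects different samples.
- **That an exposure–adverse event analysis is biased.** Protocol 2.6 gives this as a purpose of sampling, but the readable part of SAP 2.9 plans no such analysis, and the text after it is redacted.
- **That the SAP's Cmax label understates the peak.** The Tmax of about 1 h comes from fasted healthy volunteers given single doses, whereas protocol 7.2.2.6.2 places 1.5 h approximately at Cmax.

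**Conclusion.** The point holds as a minor one. While a patient is on 1 mg once daily or every other day, every correctly timed trough is excluded from the PK tables, figures and Ctrough. Nothing else in the readable documents restores it, and the December 2020 SAP does not revisit PK. This assumes that the visit-day dose is taken at the patient's usual time, as protocol 6.1.1 instructs. The number of patients is not stated, so the share of troughs affected cannot be computed. The separate post-dose mismatch rejects 25% of the protocol's accepted window and is not declared in SAP section 4.

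No efficacy or safety conclusion depends on either issue. The consequence is a 1 mg trough row that covers less than its label suggests, and the loss of some protocol-compliant post-dose values from the summaries. The LLOQ estimates rest on scaling and mono-exponential decay and serve only to judge how much the excluded values would add.

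**What to change.** In core SAP 2.2.4 and 2.9:

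1. Tie the pre-dose evaluability window to the prescribed dosing interval. Keep 9–15 h for twice-daily dosing and add stated windows around 24 h and 48 h. As an illustration, the same ± 3 h would give 21–27 h and 45–51 h, which contain the on-schedule troughs of 23.5–24 h and 47.5–48 h.
2. Summarise troughs by incident dose and regimen, without pooling regimens.
3. Reconcile the post-dose window with Table 7-7: either adopt 50–130 min, or keep 60–120 min with a reason and list it in section 4. State the 12 h sample's window in the same place, since it differs in the other direction.

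The inputs should already be held: Table 7-7, footnote b, requires the date and time of the previous dose for each trough, and the dosing record holds the dose changes. The cost is SAP wording, one regimen variable and a few small summary cells. Many every-other-day values would probably be below the LLOQ, and section 2.9 already treats those as zero and omits zeros from geometric means. The change concerns sampling windows and reporting only, not dosing.
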